### **3. OBJECTIVES AND ENDPOINTS**

The objectives and corresponding endpoints are provided in [Table 3](#).

**Table 3 Objectives and Endpoints**

Objectives	Endpoints
Primary	

 
• Assess the effect of RG7774 on the severity of DR.
 
• Evaluate the safety and tolerability of RG7774.
 
	
 
• Proportion of participants with <math>\geq 2</math> step improvement in the Early Treatment Diabetic Retinopathy Study (ETDRS) DR severity score (DRSS) from baseline at Week 36 measured in the study eye.
 
• Frequency and severity of adverse events.
 

Secondary	

 
• Assess the effect of RG7774 on progression to vision-threatening DR.
 
• Assess the effect of RG7774 on visual acuity.
 
	
 
• Incidence of anterior segment neovascularization (ASNV), new PDR, new DME, and pre-existing DME requiring intervention.
 
• Change from baseline in BCVA at Week 36 in the study eye.
 

Exploratory	

 
• Assess the effect of RG7774 on DR worsening.
 
	
 
• Proportion of participants with <math>\geq 2</math> step worsening in ETDRS DRSS from baseline at Week 36 measured in the study eye
 

 
• Assess the effect of RG7774 on DR severity at a participant level.
 
	
 
• Proportion of participants with <math>\geq 3</math> step improvement in ETDRS DRSS from baseline at post-baseline visits measured in both eyes
 
• Proportion of participants with <math>\geq 3</math> step worsening from baseline at post-baseline visits measured in both eyes.
 

**Table 3 Objectives and Endpoints (cont.)**

Objectives	Endpoints
Exploratory	

 
Assess the durability of the effect of RG7774 on DR.
 
	
 
Proportion of participants with either a stable (<math>\pm 1</math> step change), worsened (<math>>1</math> step increase) or improved (<math>>1</math> step decrease) DRSS between Week 36 and Week 48.
 

 
Assess the efficacy of RG7774 on visual acuity and anatomical outcome measures using spectral domain optical coherence tomography (SD-OCT) among eyes with DME at baseline.
 
	
 
Change from baseline in participants with DME at baseline in:               
 
BCVA (as measured on the ETDRS chart at a starting distance of 4 meters) at post-baseline visits.
 
Central subfield thickness on SD-OCT over time at post-baseline visits.
 
 
 
Proportion of participants with absence of signs of DME and normalized Central Subfield Thickness (CST) at post-baseline visits.
 

 
Assess the effect of RG7774 on visual function.
 
	
 
Change from baseline in Contrast Sensitivity at post-baseline visits in the study eye (Pelli-Robson, qCSF) or in both eyes (qCSF).
 
Change from baseline in low luminance visual acuity (LLVA) at Week 36 visit in the study eye.
 

 
Assess the effect of RG7774 on visual fields.
 
	
 
Change from baseline in mean threshold at post-baseline visits.
 
Change from baseline in point-by-point Standard Automated Perimetry at post-baseline visits.
 

 
Assess systemic pharmacokinetics and exposure-response/safety relationships of RG7774 (and its metabolite[s] as appropriate).
 
	
 
PK parameters of RG7774 (and its metabolite[s] as appropriate) in plasma and (if applicable) in optional aqueous humor.
 

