#### **4.2.3 Rationale for Primary Endpoint Assessment and Study Duration**

The primary endpoint will be the proportion of participants with a  $\geq 2$ -step improvement from baseline in ETDRS DRSS measured in the study eye at 36 weeks.

The ETDRS DRSS is a well-established scale, with step changes that are associated with different risks of long-term vision loss ([Nair et al. 2016](#)). In addition, it has already been accepted by the US regulatory agency for the label approval of ranibizumab and aflibercept ([ranibizumab USPI](#), [aflibercept USPI](#)).

Due to the systemic administration of RG7774, the primary endpoint will be supported by additional analysis at a participant level (sum of both eyes), including the response of non-study eyes with NPDR of DRSS categories 35, 43, 47 or 53 at baseline.

The evaluation at 36 weeks is considered an appropriate time point to evaluate the primary variable, as previous results in the same population have shown significant improvements as of Week 24, with treatment effects increasing up to 52 weeks ([Boyer 2019](#)).

An exploratory efficacy endpoint will be obtained 12 weeks after the last dose of the study treatment with the objective of exploring the durability of RG7774 on DRSS change, as previous trials have shown that DRSS improvements may not be maintained once treatment has stopped ([Sun et al. 2019](#)).

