**Table 6 Analysis Populations**

Population	Description
Intent-to-treat	The Intent-to-Treat (ITT) population is defined as all participants who give informed consent, are randomized, and receive at least one dose of study treatment (active or placebo). For the ITT population, data will be analyzed according to the treatment participants were randomized to. The ITT population is the primary population of interest.
Safety	The Safety population is defined as all participants who give informed consent, receive at least one dose of study medication (active or placebo) and will be grouped according to the actual treatment received. The Safety population will be used for the analyses of all safety endpoints.
Efficacy	The ITT population will be used for the analyses of all efficacy endpoints.
Pharmacokinetic	All participants in the safety population who have data from at least one post-dose sample will be included in the PK analysis population. Participants will be excluded from the PK analysis population if they significantly violate the inclusion or exclusion criteria, deviate significantly from the protocol, or if data are unavailable or incomplete which may influence the PK analysis. Excluded cases will be documented together with the reason for exclusion. All decisions on exclusions from the analysis will be made prior to database closure.

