**Table 7 Efficacy Statistical Analysis Methods**

Endpoints	Statistical Analysis Methods

Primary
 
Proportion of participants with <math>\geq 2</math> step improvement in ETDRS DRSS from baseline at Week 36 measured in the study eye.
	
Generalized Estimating Equations (GEE) with a binomial distribution taking into account repeated measures within each participant.

Secondary
 
Incidence of ASNV, new PDR, new DME, and pre-existing DME requiring intervention.
 
Change from baseline in BCVA at Week 36 in the study eye.
	
Descriptive summaries of the number, frequency and percentage of participants experiencing the types of events.
 
Analysis of variance model for longitudinal data taking into account repeated measures within each participant

Exploratory
 
Proportion of participants with <math>\geq 2</math> step worsening in ETDRS DRSS from baseline at Week 36 measured in the study eye.
	
GEE with a binomial distribution taking into account repeated measures within each participant.

Proportion of participants with <math>\geq 3</math> step improvement in ETDRS DRSS from baseline measured in both eyes at post-baseline visits.
	
Analysis performed in subgroup of ITT population with bilateral disease. Modeling will be similar as for the primary endpoint.

Proportion of participants with <math>\geq 3</math> step worsening in ETDRS DRSS from baseline measured in both eyes at post-baseline visits.
	
Analysis performed in subgroup of ITT population with bilateral disease. Modeling will be similar as for the primary endpoint.

Proportion of participants with either a stable (<math>\pm 1</math> step change), worsened (<math>>1</math> step increase) or improved (<math><1</math> step decrease) DRSS between week 36 and week 48.
	
Modeling will be similar as for the primary endpoint.

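### The exploratory durability endpoint pools participants who kept a benefit with those who never had one, so it does not isolate durability and its stable share can favour a less effective arm

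*Combined protocol and SAP*

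**What the plan says.** Table 3 lists as an exploratory objective to "Assess the durability of the effect of RG7774 on DR". The endpoint is the share of participants who are stable (within 1 step either way), worsened (more than 1 step up) or improved (more than 1 step down) in "DRSS between Week 36 and Week 48". It refers neither to baseline nor to whether the participant had improved by Week 36.

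Section 4.2.3 gives the reason for the Week 48 measurement: "previous trials have shown that DRSS improvements may not be maintained once treatment has stopped".

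Table 6 sets the denominator: "The ITT population will be used for the analyses of all efficacy endpoints". For the durability row, Table 7 says only "Modeling will be similar as for the primary endpoint". Rows of the same table that are meant for a subset say so: "Analysis performed in subgroup of ITT population with bilateral disease". The durability row has no such restriction.

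Table 7 also words the improved category differently. Table 3 has a decrease of more than 1 step and Table 7 a decrease of less than 1 step.

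**The concern.** Durability asks whether an improvement gained on treatment is still there after treatment stops. Only participants who improved can answer that. The endpoint counts everyone, which causes three problems:

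- A participant who never improved and does not move is stable, exactly like one who held a 2-step gain.
- A non-responder who progresses naturally is worsened, exactly like a responder who lost the gain.
- A participant who was 2 steps better at Week 36 and slips back 1 step is stable, although now only 1 step better than baseline and no longer a responder by the primary definition.

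At the planned response rates most of every arm are non-responders at Week 36, so they dominate the stable count. At stake is the reading of the Week 48 data in a proof-of-concept study: a reader who takes a high stable share as good durability could be misled when benefit is lost off treatment, which is the possibility Section 4.2.3 raises.

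**Working it through.** **The plan's own figure.** The documents give no figure for the durability endpoint. The response rates come from Section 9.2: 15% on placebo, 40% to 45% on active, 40 completers per group, two-sided alpha 0.10, stated power 74% to 88%. Exact enumeration of Fisher's test gives 75.5% (15% vs 40%) and 87.5% (15% vs 45%). That agrees with the plan to within 2 points, so the rates are read as intended.

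**Inputs.**

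- r, Week 36 response rate: 15%, 40% or 45% (Section 9.2), and 0% for a hypothetical arm with no responders.
- L, share of responders who lose more than 1 step by Week 48: not in the documents, varied from 0 to 100%.
- b, share of non-responders who move more than 1 step in 12 weeks: not in the documents. I use 0% and 11.5%. The second comes from the roughly 41% per year progression to vision-threatening disease in Section 4.2.1, with a constant hazard assumed: 1 − (1 − 0.41)^(12/52) = 11.5%. That event is not the same as a change of more than 1 step, so it is only a guide to scale.

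L and b are taken as equal across arms, and no responder is assumed to gain a further 2 steps or more.

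**Formula.** Stable = r(1 − L) + (1 − r)(1 − b).

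Examples at r = 40%, L = 50%:

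- b = 0: 0.40 × 0.50 + 0.60 × 1 = 80%.
- b = 11.5%: 0.40 × 0.50 + 0.60 × 0.885 = 73.1%.

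| r | L=0, b=0 | L=50%, b=0 | L=100%, b=0 | L=0, b=11.5% | L=25%, b=11.5% | L=50%, b=11.5% |
|---|---|---|---|---|---|---|
| 0% | 100% | 100% | 100% | 88.5% | 88.5% | 88.5% |
| 15% | 100% | 92.5% | 85% | 90.2% | 86.5% | 82.7% |
| 40% | 100% | 80% | 60% | 93.1% | 83.1% | 73.1% |
| 45% | 100% | 77.5% | 55% | 93.7% | 82.4% | 71.2% |

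**When the order reverses.** The stable share on placebo minus that on active is (0.40 − 0.15)(L − b). It is positive, so that placebo looks steadier, exactly when L > b. At L = 50% the gap is 0.25 × 0.50 = 12.5 points with b = 0, and 0.25 × 0.385 = 9.6 points with b = 11.5%. With L = 0 the arms tie (b = 0) or the active arm leads (b > 0).

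**The worsened category.** With L = 100% and no movement in non-responders, worsened is 15% on placebo and 40% on active. This category does register the loss. It stops being a clean count of lost responses once non-responders also progress.

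**The alternative.** The share responding at both Week 36 and Week 48, among all randomised, is r(1 − L), if retained responders stay at least 2 steps better than baseline. At L = 50% this is 0%, 7.5%, 20% and 22.5% for r = 0%, 15%, 40% and 45%, so the order follows efficacy.

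**Size of a responder subgroup.** Per 40 completers: 40 × 0.15 = 6 on placebo, and 40 × 0.40 = 16 to 40 × 0.45 = 18 on active. Exact 90% intervals for 50% retention are about 15% to 85% (3/6), 28% to 72% (8/16) and 29% to 71% (9/18). That supports description only.

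**The case against.** Four things can be said for the plan.

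- The endpoint is a three-way distribution, and nothing in the documents ranks arms on the stable share. A reader might infer that the endpoint would call an inactive drug the most durable, or that it cannot measure durability at all. The documents support neither. The reversal needs L > b, and the worsened category picks up lost responses. This stands, and it limits the point to a measure that is poorly targeted and can mislead.
- Section 9.4.2 summarises all efficacy data by group and visit in ITT, gives model estimates and odds ratios at each visit, and keeps assessments made after treatment ends. Section 8.10.3 calls Week 48 an efficacy visit. The Week 48 response against baseline may therefore already be produced. This stands in part: the plan does not name that estimate as the durability measure, and it does not split the Week 36 to 48 change by Week 36 response.
- Full details are deferred to a separate document. That document could add to the definition, but Tables 3 and 7 already fix the endpoint.
- Restricting to Week 36 responders conditions on a post-randomisation outcome. This is correct, and it is why the main measure should stay in all ITT participants.

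**Conclusion.** The concern holds in a limited form. The endpoint does not isolate durability: stable mixes kept benefit with no benefit, worsened mixes lost responses with natural progression, and a 1-step slip that ends a 2-step response is hidden. The stable share can favour the less effective arm when L > b. With half of responders losing the effect, it is 92.5% on placebo against 80% at 40% response if non-responders do not move. With b = 11.5% it is 88.5% in an arm with no responders against 73.1% at 40% response.

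These sizes rest on assumed values of L and b, taken as equal across arms. The documents supply only the response rates and the yearly progression figure. The conflict between Tables 3 and 7 on the improved category needs no assumption: a decrease of less than 1 step lies inside the stable band.

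This is a cheap improvement of minor severity. The endpoint is exploratory, and the primary endpoint and sample size are unaffected.

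**What to change.** Before unmasking:

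1. Name as the durability measure, by arm in all ITT participants, the proportion at least 2 steps better than baseline at Week 48, shown beside the same proportion at Week 36.
2. Add the proportion responding at both visits, because the Week 48 proportion alone includes newly gained responses.
3. Tabulate the existing Week 36 to 48 categories separately for Week 36 responders and non-responders, labelled as description only.
4. Reconcile the improved category in Table 7 with Table 3.
5. Have the planned missing-data document cover Week 48. Section 8.10.3 asks participants who stop treatment early to return only for the safety follow-up, so their Week 48 assessment may be absent.

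The cost is one extra table. The stated endpoint already requires DRSS at Week 48, so no visit or assessment is added. The limit is the small descriptive subgroups, about 6 placebo and 16 to 18 active responders per 40 completers.

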**Table 3 Objectives and Endpoints (cont.)**

Objectives	Endpoints
Exploratory	

 
Explore the effect of RG7774 on markers of kidney function.
 
	
 
[REDACTED]
 

 
Explore potential effects of RG7774 on glycemic status.
 
	
 
Change from baseline in blood levels of HbA1c.
 

 
Assess the effect of RG7774 on systemic biomarkers of inflammation and disease in peripheral blood.
 
	
 
[REDACTED]
 

 
[REDACTED]
 
	
 
[REDACTED]
 

 
[REDACTED]
 
	
 
[REDACTED]
 

 
[REDACTED]
 
	
 
[REDACTED]
 

 
To contribute to the development and/ or evaluation of advanced analytics tool (artificial intelligence based tool) for the assessment of clinically relevant features
 
	
 
Performance of the advanced analytic tools
 

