### **CONCOMITANT MEDICATIONS**

#### **Permitted Therapy**

Participants should not change their existing stable treatment for DM and its consequences during the study, unless it is required for the treatment of an AE or as a result of potential DDI. Potential DDI arising from co-administration of other drugs have been investigated in healthy volunteers only. Therefore, changed or new concomitant medication in general should be limited to the medical need of the participant and the medical judgement of the investigator, in consultation with the Sponsor.

The Investigator should be aware of the potential for DDI when prescribing concomitant medications which are inhibitors or inducers of CYP3A and/or CYP2C19, or are substrates of CYP3A, OCT2, MATE1, MATE2-K, P-gp, and/or BCRP and should carefully monitor the tolerability and safety of RG7774. The Sponsor has included two visits to monitor if there is a need to adjust the dose of warfarin, if applicable.

Therapies permitted for either eye in case of incidence or progression of DME/DR are:

- Laser (grid or focal) and/or approved anti-VEGF (except brolocizumab, if applicable), and/or approved steroids in case of worsening DME which requires treatment for participants presenting with DME at baseline.

- Laser (grid or focal) and/or approved anti-VEGF (except brolucizumab, if applicable), and/or approved steroids in case of incident DME requiring treatment
- Laser (pan-retinal), vitrectomy and/or approved anti-VEGF (except brolucizumab, if applicable) in case of incident PDR.

The administration of these permitted therapies will not automatically result in treatment discontinuation and participants should continue in the study as described.

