### **6.5.1 Permitted Therapy**

Participants should not change their existing stable treatment for DM and its consequences during the study, unless it is required for the treatment of an AE or as a result of potential DDI. Potential DDI arising from co-administration of other drugs have been investigated in healthy volunteers only. Therefore, changed or new concomitant medication in general should be limited to the medical need of the participant and the medical judgement of the investigator, in consultation with the Sponsor.

For all concomitant medication, therapeutic drug monitoring has to be done at the judgement of the investigator to the uses and administration requirements of the product/package insert.

The Investigator should be aware of the potential for DDI when prescribing concomitant medications which are inhibitors or inducers of CYP3A and/or CYP2C19, or are substrates of CYP3A, OCT2, MATE1, MATE2-K, P-gp, and/or BCRP and should carefully monitor the tolerability, safety and efficacy of the respective medication. The Sponsor has included two visits to monitor if there is a need to adjust the dose of warfarin, if applicable (see SoA in Section 1.3 and Section 8.10.2).

Due to the observed CYP3A enzyme induction of RG7774 at doses of 200 mg and 300 mg administered once-daily, caution should be exercised when co-administering drugs predominantly metabolized by CYP3A and/or the CYP2C9 family, including oral contraceptives or hormonal replacement therapeutics. Therefore, female participants of childbearing potential taking hormonal contraceptives must supplement with a barrier method.

Therapies permitted for either eye in case of incidence or progression of DME/DR are:

- Laser (grid or focal) and/or approved anti-VEGF (except brolucizumab, if applicable), and/ or approved steroids in case of worsening DME which requires treatment for participants presenting with DME at baseline.
- Laser (grid or focal) and/or approved anti-VEGF (except brolucizumab, if applicable), and/ or approved steroids in case of incident DME requiring treatment
- Laser (pan-retinal), vitrectomy and/or approved anti-VEGF (except brolucizumab, if applicable) in case of incident PDR.

The administration of these permitted therapies will not automatically result in treatment discontinuation and participants should continue in the study as described in Section 7.

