### 9.4.2 Efficacy Analyses

For the primary and exploratory efficacy analyses, see [Table 7](#).

All efficacy data will be summarized by randomized treatment group and visit for the ITT population.

Participants in whom any of the events (i) to (iii) described in Section 6.5.3 occur in either eye, or participants who require rescue treatment prior to the week 36 assessment will still be considered as completing participants and will enter the analysis as non-responders at the visit at which the event occurs as well as all subsequent visits.

The primary endpoint will be analyzed using GEE with a binomial distribution using a logit link function for odds ratios and unstructured covariance. In case of convergence issues, an alternative covariance structure will be used. The model will include categorical covariates for treatment group, visit, and visit by treatment group interaction term. Also the baseline stratification factors will be added. Least squares means on the probability scale for each treatment group with the corresponding 90% confidence intervals and odds ratios relative to the placebo group will be computed for each visit. Full details of the statistical analysis will be described in a separate document prior to any unmasking of the study.

In accordance with the ITT principle, assessments at all visits will be included in the analysis. This includes any assessments made at visits while the participant is on randomized study treatment as well as any assessments made at visits after randomized study treatment has been terminated.

If visits occur as described in Section 1.3, a response assessment at week 36 will be available for all participants. Despite best efforts, there may be missing response assessments at week 36 (e.g., for participants withdrawing consent or being lost to follow-up). *The statistical methodology to deal with missing data will be described in a separate technical document prior to any unmasking of the study.*

The proposed methodology is known to render unbiased effect estimates only under the restrictive missing completely at random assumption (Liang and Zeger, 1986). Therefore, if the amount of total missing data (across patients and visits) exceeds 10% of all expected data, sensitivity *analyses* will be carried out (Molenbergs and Verbeke, 2005).

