**Table 7 Efficacy Statistical Analysis Methods (cont.)**

Change from baseline in participants with DME at baseline in:
 
 
• BCVA (as measured on the ETDRS chart at a starting distance of 4 meters) at post-baseline visits.
 
• Central subfield thickness on SD-OCT at post-baseline visits.
 
 
Proportion of participants with absence of signs of DME and normalized CST over time
	
Analysis of variance model for longitudinal data taking into account repeated measures within each participant.

Change from baseline in Contrast Sensitivity at post-baseline visits in the study eye (Pelli-Robson, qCSF) or in both eyes (qCSF).
	
Analysis of variance model for longitudinal data taking into account repeated measures within each participant.

Change from baseline in LLVA at Week 36 visit in the study eye.
	
Analysis of variance model for longitudinal data taking into account repeated measures within each participant.

Absolute change from baseline in mean threshold and in point-by-point Standard Automated Perimetry at post-baseline visits.
	
Analysis of variance model for longitudinal data taking into account repeated measures within each participant.

PK parameters of RG7774 (and its metabolite(s) as appropriate) in plasma and (if applicable) in optional aqueous humor.
	
Descriptive summaries of the PK parameters (e.g., <math>C_{max}</math>, AUC, etc.)

Change from baseline in blood levels of HbA1c.
	
Descriptive summaries by treatment group and visit

Performance of the advanced analytic tools
	
Analysis of the exploratory efficacy endpoints

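### The exploratory HbA1c endpoint is planned as descriptive summaries only, with no baseline-adjusted dose-placebo estimate or interval, while the other readable continuous change-from-baseline endpoints get a longitudinal model

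*Combined protocol and SAP*

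**What the plan says.** Table 3 gives, among the exploratory objectives, "Explore potential effects of RG7774 on glycemic status". The endpoint, repeated in Table 7, is "Change from baseline in blood levels of HbA1c", and its whole stated method is "Descriptive summaries by treatment group and visit".

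For BCVA (secondary), and for BCVA and central subfield thickness in participants with DME at baseline, contrast sensitivity, low-luminance acuity and perimetry (exploratory), Table 7 names a different method: "Analysis of variance model for longitudinal data taking into account repeated measures within each participant".

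Section 9.4.2 sets out the primary GEE with treatment, visit and their interaction, and says "Also the baseline stratification factors will be added". HbA1c is neither a stratification factor nor a listed covariate. The same section reports 90% confidence intervals, includes assessments from all visits (also those after study treatment has ended), and defers detail: "Full details of the statistical analysis will be described in a separate document prior to any unmasking of the study".

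Section 6.5.1 asks that diabetes treatment stay stable "unless it is required for the treatment of an AE or as a result of potential DDI". Under Table 8 and Section 9.6, concomitant medications are summarised and listed.

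**The concern.** The objective concerns an effect of the drug, but the plan produces only a set of arm-level numbers. Section 9.4.2 already says that all efficacy data will be summarised by randomised group and visit, so the HbA1c row adds nothing to that default. A reader who wants to know how far HbA1c moved on each dose relative to placebo, and how uncertain that is, would have to derive it from the tables. Whether that is possible depends on which statistics are printed.

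The question has some interest here. Section 2.2.1 attributes retinopathy partly to sustained raised glucose, entry now allows HbA1c up to 12%, and diabetes treatment may change during the study for stated reasons. A clear HbA1c contrast is therefore useful context when DRSS results are discussed.

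**Working it through.** **Comparison within Table 7.** Exploratory status does not explain the difference in method, because contrast sensitivity, low-luminance acuity and perimetry are also exploratory, and perimetry is optional. The data would support a model. Table 1 shows HbA1c at screening and repeatedly afterwards, and Table 2 keeps it after rescue treatment. Section 9.4.1 defines baseline as the last non-missing value up to first dosing.

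**The plan's own figures.** None is stated for HbA1c. The only input taken from the plan is 40 completers per group (Section 9.2; 45 × 0.90 = 40.5).

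**Assumed inputs.** HbA1c SD s = 1.5 points, equal at baseline and Week 36; baseline to Week 36 correlation r = 0.5 to 0.8; normal quantile 1.645 for a 90% interval. The documents give neither s nor r.

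**Formulas, one dose against placebo at Week 36:**

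- Unadjusted difference in mean change: variance = (2/n) × 2s²(1 − r).
- Baseline-adjusted difference: variance = (2/n) × s²(1 − r²).
- Variance ratio, adjusted to unadjusted: (1 + r)/2.

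**Numbers for r = 0.5, n = 40:**

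- Unadjusted: 0.05 × 2 × 2.25 × 0.5 = 0.1125; half-width 1.645 × √0.1125 = 0.552.
- Adjusted: 0.05 × 2.25 × 0.75 = 0.0844; half-width 1.645 × √0.0844 = 0.478.

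| r (assumed) | Half-width, mean change | Half-width, adjusted | √((1 + r)/2) | Interval narrower by |
|---|---|---|---|---|
| 0.5 | 0.552 | 0.478 | 0.866 | 13% |
| 0.7 | 0.427 | 0.394 | 0.922 | 8% |
| 0.8 | 0.349 | 0.331 | 0.949 | 5% |

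Half-widths scale with s, and the percentages do not depend on it. At s = 1.0 every half-width is two-thirds of the value shown (0.368 against 0.319 at r = 0.5).

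**Is the interval informative at this sample size?** Start instead from an assumed SD of the change of 0.8 to 1.5 points and a covariate correlation ρ of 0 to 0.7. Then half-width = t × SD × √(1 − ρ²) × √(2/40), with t on 77 degrees of freedom. This gives about 0.21 to 0.56 points, for example 0.32 at SD 1.0 and ρ = 0.5.

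**The case against.** The case for leaving the row alone has substance.

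- **The objective is to explore potential effects.** Many of the modelled objectives are worded as assessing an effect, and Section 9.5 calls the study hypothesis-generating. Descriptive reporting is permissible. It is also used for the secondary progression endpoint and for PK, although neither is a continuous change from baseline. This stands, and it keeps the point minor.
- **The comparison is with ocular endpoints only.** The kidney and inflammation endpoints in Table 3 and all of Section 9.4.5 are blacked out, so it cannot be judged whether HbA1c is treated differently from other systemic measures. This stands as a limit.
- **The separate analysis document may add a model.** It may, but nothing in the available text commits to one. It is also a convenient place for the change.
- **The precision gain is small.** At s = 1.5 it is between 0.02 and 0.07 points of half-width. This is correct. The larger benefit is having a pre-specified contrast at all.

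A reader might also draw three stronger conclusions, which the documents do not support:

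- **That the planned summaries ignore baseline or the repeated visits.** They do not. Change from baseline subtracts each participant's own value, and every visit is reported. Only covariate adjustment, a contrast and an interval are missing.
- **That the protocol describes a glycemic effect of RG7774.** Section 6.5.1 warns of interactions, "Due to the observed CYP3A enzyme induction of RG7774 at doses of 200 mg and 300 mg administered once-daily", but the examples it names are hormonal products. Section 2.2.2.1 mentions metformin as a transporter probe and gives no result. A route to altered glycemia is inference.
- **That an HbA1c contrast would show whether a DRSS effect runs through glycemia.** It would show only whether HbA1c moved. Mediation needs a further analysis and further assumptions, and no objective asks for it.

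**Conclusion.** The point holds as a minor gap. An exploratory objective about a possible drug effect has no planned estimate of that effect, although the protocol already uses a suitable model for its other readable continuous endpoints. The planned mean changes are unbiased under randomisation, so nothing planned is wrong. The quantified gain is a 90% interval about 13% to 5% narrower for r from 0.5 to 0.8. That range rests on the assumed correlation, equal variances at the two times and complete data at Week 36. The half-widths in HbA1c points also rest on the assumed SD. The primary GEE, the 135 participants and the stated 74% to 88% power are untouched.

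**What to change.** In the HbA1c row of Table 7, or in the separate analysis document before any unmasking:

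- Keep the descriptive summaries.
- Add the longitudinal repeated-measures model used for the other continuous endpoints, with baseline HbA1c, the stratification factors, treatment, visit and treatment by visit. Include all visits, as Section 9.4.2 requires, also those after study treatment has ended.
- Report each dose minus placebo at Week 36 with a 90% interval, labelled exploratory.
- As context, tabulate by arm the participants whose diabetes medication was started, stopped or changed. The concomitant-medication data already collected are enough for this.
- State that the contrast will not be read as evidence of mediation of a DRSS effect.

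Do not add a repeat of the model that drops HbA1c values after a change in diabetes medication, or label it supportive only. Such a change happens after randomisation and may be driven by HbA1c itself, and dropping the values departs from the all-visits rule.

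The cost is a wording change, one extra model and one extra table. No new visits, samples or participants are needed.
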